15.1.4. SENSITIVITY ANALYSIS OF PRIMARY EFFICACY VARIABLE(S)

In order to addressing robustness of the primary analysis results of primary efficacy endpoint, several sensitivity analysis approaches are proposed:

- Above statistical analysis method will be conducted using the PPS population.
- Above statistical analysis method will be conducted using the FAS population with multiple imputation (MI) method, last observation carried forward (LOCF) method, and next observation carried back (NOCB) method for primary efficacy endpoint.
- Different statistical models. An analysis of variance (ANCOVA) model on primary efficacy endpoint (wound volume reduction rate) as dependent variables with debridement (occurred before first application or not), treatment group, center, treatment-by-center interaction and treatment-by-wound size interaction (if the interaction effect is not statistically significant, then it will be removed from the final model) as fixed factors, wound size (wounds surface area, $<15\text{cm}^2$ (ref), $15\text{-}30\text{cm}^2$, and $>30\text{cm}^2$) as covariate will be performed using the PPS population. The following statistics will be presented: LS Means, difference of the LS Means as well as its 95% CI, P-value for LS Mean difference, -value of treatment group, center, treatment-by-center interaction, treatment-by-wound size interaction (present only if interaction effect is significant), debridement and wound size.

15.2. SECONDARY EFFICACY VARIABLES & DERIVATIONS

FAS population will be used for secondary efficacy variables such as the time to completion of wound bed preparation, rate of wound area reduction, and changes in granulation tissue.

15.2.1. MISSING DATA METHODS FOR SECONDARY EFFICACY VARIABLES

Subjects in the study whose wound area reduction rate at effective visit (after study treatment 14 days or deemed ready for closure before 14 days) is unknown will be imputed. The multiple imputation (MI) method will be used for the FAS analysis. The last observation carried forward (LOCF) method and next observation carried back (NOCB) method will be used to impute missing area measures for each subject as a sensitivity analysis.

Missing value for other secondary endpoints for example time to wound bed preparation will not be imputed and will be treated as missing.

15.2.2. TIME TO COMPLETION OF WOUND BED PREPARATION (UNIT: DAY)

Define: Duration from the randomization until target wound ready for closure by secondary intervention judged by the investigator.

Evaluation time point: Day of Randomization (Day 0) and End of Treatment Visit.

Measurement: the date deemed ready for closure by secondary intervention - the date of the randomization + 1.

Statistical method: the difference between investigational group and control group will be assessed by Kaplan-Meier method and log rank test, and with covariate adjustment using the Cox proportional hazard regression and Wald Chi-Square.

Censor data define: .

The duration of treatment for a patient is considered right-censored if it meets one of the below conditions:

- Patient completed the study but the completion category was “The treatment duration up to 14 Days”, and the subjects’ target wound not ready for closure before end of treatment visit. Patient’s will be censored on day of end of treatment visit.
- Patient prematurely withdraws from the study and the subjects’ target wound not ready for closure before end of treatment visit, patients will be censored on the date of their last 3D wound imaging assessment.
- Subjects with no post-baseline 3D imaging wound measurements assessments will be censored on the day of randomization (i.e. Day 0).

Here, duration of treatment for a patient is defined as the date of the last wound measurements assessments minus the date of randomization plus one.

The Kaplan-Meier analysis of the time to completion of wound bed preparation will be performed, the Kaplan-Meier plot will be presented. The Cox proportional hazard regression with covariates from primary endpoints will be used to estimate the hazard ratios for effect of treatment factor.

The results of the log-rank test for the comparison of investigational group and control groups will be expressed by a Chi-square statistic and P-value, The results of cox proportional hazard regression will be present by HR statistic and P value, the P-value <0.05 will be considered as statistically significant.

An example of SAS code for cox proportion regression model is provided:

```
Proc phreg;
Class treat(ref=control) center(ref=sitel1) woundtype(ref=1);
Model time*completion of wound bed preparation(yes) =treat center treat*center woundtype
/risklimits;
Run;
```

Additional analyses will include summary statistics of the number of events and censored values, median time of duration as well as its 95% confidence interval will also be presented. Listings will be presented and sorted by treatment group, subject id.

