### **3.1.3.1 Summary of Animal, in Vitro Studies and Clinical Trials**

While there is broad acceptance and a large body of evidence that supports NPWTi-d (with V.A.C. VERAFLDTM Dressing Kit) as an important tool in aiding wound healing. Most evidence include animal studies, expert opinion, case reports, case series and involving prospective treatment groups compared with control.

In 2012, Anthony et al, compared continuous and periodic wound instillation in conjunction with negative pressure wound therapy using an agar-based model. Continuous instillation at a rate of 30 cc/hour with negative pressure showed isolated exposure of instillation fluid to wound beds in agar wound models with and without undermining and tunneling. In contrast, periodic instillation illustrated uniform exposure of the additive to the entire wound bed including undermined and tunnel areas, with increased staining with each instillation cycle. These findings suggest that periodic instillation facilitates more uniform exposure throughout the wound, including tunnels and undermining, to instillation solutions, thereby providing therapy consistent with the

clinician-ordered treatment.

In 2013, Lessing et al, found that a greater reduction in wound area and perimeter in NPWTi-d wounds compared to all NPWT wounds ( $P < .05$ ) by 3D images Analysis on porcine excisional wounds.

In 2011, a post marketing study using VAC. VERAFLTM Dressing in operatively debrided wounds, the results showed that there was no statistically significant difference in the time to wound deemed ready or closure or coverage between NPWTi-d (n=71) and NPWT(n=66) subjects (mean 6.8 vs 6.3 days, median 6 vs 5 days, respectively;  $p = 0.7105$ ) in the Per-Protocol Population (NCT01867580).

In 2013, Brinkert et al, collected 131 patients treated with V.A.C. VERAFLTM Dressing. Mean duration of NPWTi-d was 12~19 days. 98% of the cases, the wounds were closed after debridement and following the use of NPWTi-d.

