### **5.5.2.4 End of Treatment Visit**

The following data will be collected before any subsequent treatment:

(1) Physical exam.

(2) Blood routine examination

RBC count, WBC count, Hemoglobin, Platelet.

(3) Wound clinical assessments.

- (4) Stop study treatment and remove NPWT dressing.
- (5) Digital/3D wound imaging (prior to commencing any subsequent treatment).
- (6) Concomitant medications

All medications the subject is taking during the study.

- (7) Collect and assess AEs/SAEs.
- (8) Device deficiencies.

**Note:** Visit will be conducted when subject's target wound is deemed ready for closure by investigator or treatment duration up to 14 Days (+/-1 Day). If the target wound can be closed judged by investigator within 14 days since initial treatment, the closure date and method are to be recorded.

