#### **5.5.3 Specification Direction for Use of Device**

- (1) For subjects with multiple wounds, the target wound can only be treated with the randomly assigned device and the other wounds will receive the standard wound treatment in the institution.
- (2) Placing the dressings in the target wound directly following the definitive surgical debridement (if applicable) according to the investigational or control device IFU.
- (3) During the subject's hospital admission, subjects will receive their assigned study

treatment without interruption until the wound is deemed ready for closure or up to 14 days (whichever occurred first).

- (4) For the investigational group, instillation solution (only normal saline) will be refilled by related staff as often as required. Canister changes for each group will be performed by related staff as often as required.
- (5) Dressing change frequency will be determined by the investigator based on the wound condition and clinical experience, and the frequencies of investigational and control group devices are the same (48-72h one change).
- (6) If the wound has been deemed ready for closure, study treatment will stop and subjects will then transition to receive institutional standard wound treatment at the discretion of the investigator.
- (7) If the secondary intervention condition of the target wound is not met after 14 days of treatment with the investigational device, the patient will receive further clinical treatment judged by the investigator re-evaluation according to the standard wound treatment in the institution.

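### The Cox model for time to wound bed preparation names no method for tied event times; on the software default the adjusted hazard ratio would be about 2-3% too close to 1 and its Wald test mildly conservative

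*SAP*

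**What the plan says.** - **Endpoint and time scale.** SAP 15.2.2 measures time as "the date deemed ready for closure by secondary intervention - the date of the randomization + 1", so it takes whole-day values. Protocol 5.3.1.2 defines it the same way and lists it as the first secondary endpoint.
- **Follow-up.** The End of Treatment Visit is tied to readiness or to "treatment duration up to 14 Days (+/-1 Day") (Protocol 5.5.2.4).
- **Analysis.** SAP 15.2.2 plans Kaplan-Meier curves and a log-rank test, then a comparison "with covariate adjustment using the Cox proportional hazard regression and Wald Chi-Square", with P<0.05 counted as significant. Protocol 6.5.1 names only Kaplan-Meier and log-rank specifically for this endpoint.
- **Code.** The SAP introduces the code with "An example of SAS code for cox proportion regression model is provided". The model line is "Model time*completion of wound bed preparation(yes) =treat center treat*center woundtype", and its only option is risklimits. No TIES= option appears in the code, and no tie method appears in the text.
- **Dressing changes.** Protocol 5.5.3 leaves the frequency to the investigator and adds that "the frequencies of investigational and control group devices are the same (48-72h one change").
- **When readiness is judged.** Protocol 5.5.2.4 says "Visit will be conducted when subject's target wound is deemed ready for closure by investigator". No text limits that judgement to a dressing change.

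**The concern.** The Cox partial likelihood is simplest when no two subjects have their event at the same time. Here up to 170 subjects can have events on only about 14 distinct days, and perhaps fewer if readiness tends to be declared at dressing changes. The handling of ties then affects the answer.

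Breslow's approximation compares every tied event with the full risk set, as if none of the others who failed that day had yet left it. This is accurate when few subjects fail at once and poor when a sizeable share of the risk set does.

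At stake is the adjusted HR, with its confidence interval and Wald p-value, for a reported secondary endpoint. Attenuation works in both directions, so a benefit and a delay are both understated. A delay is not far-fetched: the earlier study in Protocol 3.1.3.1 reported "mean 6.8 vs 6.3 days, median 6 vs 5 days, respectively" for instillation and standard therapy, a numerically longer time with instillation, though not statistically significant.

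**Working it through.** **The plan's own figure.** The plan gives no HR, event count or power for this endpoint, so there is nothing to reproduce. The sample size in Protocol 6.1.1 and SAP 5.4 concerns wound volume only.

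**Inputs from the documents:** up to 85 subjects per arm (Protocol 6.1.1), whole-day times, 14 days of treatment, and dressing changes every 48-72 h.

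**Assumptions:** exponential readiness times; control median 6 days (10 days as a variant), guided by the medians of 6 and 5 days in Protocol 3.1.3.1; true HR 1.5; Breslow as the software default.

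**Step 1. How heavy are the ties?** Expected events by day 14 are 85 × (1 − 2^(−14/6)) = 68.1 in the control arm and 85 × (1 − 2^(−1.5×14/6)) = 77.5 in the investigational arm. That is about 146 events on at most 14 distinct days. The first day alone is expected to hold 85 × (0.1091 + 0.1591) = 22.8 events (proportions from Step 2). Whole-day recording is enough to make ties heavy, without any assumption about dressing changes.

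**Step 2. What does Breslow estimate?** At one tied time, with d events among n at risk in each arm, the Breslow contribution is maximised at exp(β) = (d1/n1) ÷ (d0/n0). This is the ratio of the proportions failing in the interval, not the ratio of hazards. For interval width w and a 6-day median, p0 = 1 − 2^(−w/6) and p1 = 1 − 2^(−1.5w/6):

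| Recording interval | p0 | p1 | p1/p0 | Shortfall from 1.5 |
|---|---|---|---|---|
| 1 day | 0.1091 | 0.1591 | 1.458 | 2.8% |
| 2 days, same grid for all | 0.2063 | 0.2929 | 1.420 | 5.4% |
| 3 days, same grid for all | 0.2929 | 0.4054 | 1.384 | 7.7% |

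With a 10-day median the 1-day ratio is 0.0987/0.0670, about 1.47, and the 3-day ratio is 0.2680/0.1877, about 1.43. The attenuation does not depend on the number of subjects.

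**Step 3. Simulation** (85 per arm, control median 6 days, true HR 1.5):

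| Recording | Breslow HR | Wald power, Breslow | Wald power, Efron |
|---|---|---|---|
| Whole days | 1.48 | 66% | 71% |
| Each subject's own 2-3-day gaps | 1.45 | 61% | 68% |
| One 3-day grid for all | 1.40 | 53% | 70% |

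Efron's HR was 1.50-1.52 throughout. A separate set of 2,000 trials per setting gave Breslow HRs of 1.46 (individual gaps), 1.42 (2-day grid) and 1.39 (3-day grid), against 1.51, 1.50 and 1.49 with Efron. Breslow power there was 64% (whole days), 62% (individual gaps) and 51% (3-day grid), against about 67-69% with Efron. These runs agree with Step 2 within simulation error.

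**Step 4. Standard error and test size.** The printed standard error was the same under both methods, at 0.1675-0.1677. With 8 assumed centres and 3 wound-size classes in the model, Breslow's was very slightly smaller (0.1759 against 0.1766 with individual gaps). It exceeds only the sampling spread of the attenuated Breslow estimate itself, by a ratio of 1.05-1.26 at a 6-day median. For that reason the Wald test rejects too rarely under no effect: 2.4-3.5% at a 6-day median and 2.8-4.9% at 10 days, against a nominal 5%.

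**Step 5. Scale.** On the log scale the 1-day shortfall is ln 1.5 − ln 1.458 = 0.405 − 0.377 = 0.028. Divided by a standard error of 0.1675, that is about 0.17 of one standard error.

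**The case against.** Much of the case on the other side stands.

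- **The log-rank test already protects detection of a difference.** It does not depend on the Cox tie option. In simulation its power matched Efron-based Cox: 70.1% against 69.8% for whole days, and 66.2% for both with individual gaps. A reader might infer that the trial would miss a real difference in time to readiness because of this omission. The documents do not support that, since SAP 15.2.2 keeps the log-rank test. Only the adjusted HR, its interval and its Wald test are affected.
- **The SAP does not prescribe Breslow.** It never names the method, and the code is labelled an example and written schematically. Still, nothing in the SAP would lead a programmer to choose otherwise.
- **Readiness is not confined to dressing changes.** A reader might infer from the 48-72 h interval that the wound can be judged only then. Protocol 5.5.2.4 lets the investigator's judgement trigger the visit, so clustering is plausible but not stated.
- **The larger figures need a common 3-day grid.** Protocol 5.5.3 leaves the interval to the investigator within 48-72 h, so subjects will not share one schedule.
- **An inflated standard error is also a tempting reading.** Step 4 shows that the printed value hardly depends on the tie method.
- **The simulation is not the exact planned model.** It uses the maximum of 170 subjects without the roughly 25% drop-out of Protocol 6.1.3, and omits the treatment-by-center term. Drop-out would lower power under both methods. If the interaction is kept, the treatment coefficient refers to the reference center rather than to an overall HR.

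What remains is a small attenuation, always in the same direction, in a reported estimate.

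**Conclusion.** The point holds as a minor one. SAP 15.2.2 leaves the tie method open for data that will be heavily tied, and the example code would fall back on a default that biases the adjusted HR toward 1. At a true HR of 1.5 the realistic size is about 2-3% of the HR and about 5 to 7 points of Wald power (71 − 66 and 68 − 61). A shortfall of about 7-8% of the HR (1.39-1.40) belongs to the extreme common 3-day grid. The primary non-inferiority conclusion is untouched.

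The size rests on Breslow being the default, on exponential readiness times and on a 6-day control median. A 10-day median makes it smaller, and a larger true effect makes it bigger: a true HR of 2.0 came out at 1.70-1.90 across the tied recording schemes. The direction was the same in every tied scenario with a real effect.

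**What to change.** In SAP 15.2.2, state in the text that ties in the Cox model are handled by Efron's method, and add TIES=EFRON to the options on the PHREG MODEL statement. TIES=EXACT would also serve, as would a discrete-time model with a complementary log-log link. The log-rank analysis needs no change.

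The cost is one sentence and one option, settled before database lock. It needs no new data and has no evident downside. The printed standard error will stay essentially where it was; the gain is an HR close to its true value and a Wald test close to its nominal level.

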### **5.2.3 Criteria and Procedures for Subject Withdrawal**

#### **1) Dropout Criteria**

Definition: A subject in the clinical trial who for any reasons fails to continue in the study until the last visit required of him/her by the study protocol.

If meet the following situations:

- Lost to follow-up.
- Subjects withdraw their informed consent and voluntarily withdraw from the trial:  
Subjects could withdraw from the trial voluntarily if they could not endure the AE, think the treatment is not effective, and want to take other treatments or without any reason.
- When the investigator judged that the risk is greater than the benefit if subject continues to participate in the trial, or the subject cannot continue the clinical trial

in the following conditions, for example a subject has abnormal organ dysfunction, allergic reaction, poor compliance, exacerbations, or a SAE needed to stop the trial treatment, and the subject should withdraw from the trial.

- The subject's target wound needs other treatment and should withdraw from the trial.
- If the target wound condition worsens (such as infection aggravated, anaerobic bacteria infection, etc.) in the use of investigational dressing or control dressing during the process of NPWT, after the investigator's evaluation of wound and treatment result, and if the surgical debridement is needed again, the NPWT will be stopped, the end of study assessments completed and the subject withdrawn from the study, then the target wound will be opened and debrided repeatedly, until the next intervention (such as delayed healing, surgical closure, graft et al) can be carried out.

Subjects have the right to withdraw from the trial at any time without any reason.

For all subjects terminate the trial in advance, the investigator should make every effort to obtain the reasons of withdrawal, e.g. AEs, unsuccessful correction therapy, withdrawing from the trial based on the investigator's judgment or other reasons, which should be recorded on the source documents. Subjects withdrawing from treatment in the trial should complete withdraw visit according to the schedule of visit procedure.

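### The time-to-readiness curve and median overstate readiness, because withdrawals for wound failure are censored in the same way as ordinary losses

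*SAP*

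**What the plan says.** SAP 15.2.2 defines the endpoint as "Duration from the randomization until target wound ready for closure by secondary intervention judged by the investigator". Treatment groups are to be "assessed by Kaplan-Meier method and log rank test, and with covariate adjustment using the Cox proportional hazard regression and Wald Chi-Square", and the median time is reported with a 95% confidence interval. A subject who completes 14 days without readiness is censored at the end of treatment visit. For a subject who withdraws prematurely with the wound not ready, "patients will be censored on the date of their last 3D wound imaging assessment". A subject with no post-baseline image is censored at Day 0. The rule does not distinguish reasons for withdrawal.

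Protocol 5.2.3 includes failures of treatment among its dropout criteria. For a worsening wound it says that "if the surgical debridement is needed again, the NPWT will be stopped, the end of study assessments completed and the subject withdrawn from the study". A separate criterion reads "The subject's target wound needs other treatment and should withdraw from the trial". The same list includes exacerbation, and voluntary withdrawal by subjects who consider the treatment ineffective and want another.

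SAP 15.2 states that the "FAS population will be used for secondary efficacy variables such as the time to completion of wound bed preparation", so these subjects enter the analysis. SAP 15.2.1 says that missing values of time to wound bed preparation "will not be imputed and will be treated as missing", which does not count them as failures either. Neither document gives a competing-risk method or a sensitivity analysis for this endpoint.

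**The concern.** Kaplan-Meier estimation assumes that a censored subject would have gone on to reach the event at the same rate as those still at risk. That may be fair for loss to follow-up. It is not fair for a subject withdrawn because the wound deteriorated, since the reason for censoring is close to the opposite of the event.

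The rule is also uneven. A subject not ready at Day 14 stays in the risk set throughout, while one who fails on Day 3 leaves it on about Day 3. Protocol 5.5.2.5 schedules imaging at the withdrawal visit, so the last image normally falls at or near the failure.

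Two results are at stake. The first is the level of the readiness curve and its median, which a reader will take as the chance and the time of becoming ready. The second is the between-arm comparison, which will not register a difference in failures. Both the readiness decision and the withdrawal decision rest with the investigator in an open-label trial, so failure-type withdrawals could differ by arm. The blinded image assessor makes neither decision.

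**Working it through.** **The plan's own figure.** The documents give no event count, hazard ratio or power for this endpoint. The only design figure is 128 evaluable subjects for the primary endpoint (Protocol 6.1.1: margin 20%, SD 40%, one-sided 0.025). A noncentral t calculation gives 80.1% power at 64 per arm, so the figure reproduces. It does not bear on this point.

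**Inputs.**
- Follow-up is up to 14 days (Protocol 5.1.1).
- Readiness and failure rates are assumptions. As an anchor, Protocol 3.1.3.1 reports median times to readiness of 6 and 5 days in an earlier study.
- The 25% drop-out rate in Protocol 6.1.3 covers every exclusion from the primary analysis. It is only an upper guide to failure-type withdrawal.

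**Level of the curve, closed form.** Take constant hazards r for readiness and w for failure withdrawal.
- What the SAP rule estimates at Day 14: 1 − exp(−14r).
- Proportion actually becoming ready on treatment: r/(r+w) × [1 − exp(−14(r+w))].
- Proportion withdrawn for failure: w/(r+w) × [1 − exp(−14(r+w))].

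Set the SAP estimate at 85%, so r = −ln(0.15)/14 = 0.1355. Solve for w to give the stated proportion withdrawn.
- 5% withdrawn: w = 0.0083, and 0.942 × 0.866 = 81.6% ready.
- 20% withdrawn: w = 0.0381, and 0.781 × 0.912 = 71.2% ready.

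| Withdrawn for failure | SAP estimate | Actually ready | Overstatement | Median, SAP v cumulative incidence (days) |
|---|---|---|---|---|
| 5% | 85% | 81.6% | 3.4 points | 5.1 v 5.3 |
| 10% | 85% | 78.2% | 6.8 points | 5.1 v 5.4 |
| 15% | 85% | 74.7% | 10.3 points | 5.1 v 5.6 |
| 20% | 85% | 71.2% | 13.8 points | 5.1 v 5.9 |
| 25% | 85% | 67.6% | 17.4 points | 5.1 v 6.2 |

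Over 5% to 25% withdrawn, the overstatement runs from 2.4 to 12.7 points if the SAP estimate is 70%, and from 4.2 to 21.8 points if it is 95%. This calculation assumes nothing about what happens after withdrawal.

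**Level of the curve, simulation.** Take median readiness of 6 days among non-failures and failures withdrawn on days 2 to 6. The actual proportion ready is (1 − failure proportion) × (1 − 2^(−14/6)). That is 0.95 × 0.802 = 76% at 5% failures and 0.80 × 0.802 = 64% at 20%. The SAP rule reads about 80% and 77% to 78%.

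**Between-arm comparison.** Same simulation, 85 per arm, identical readiness hazard among non-failures. The last column also assumes that failures never become ready by Day 14.

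| Failures, arm A v arm B | HR (A v B), SAP rule | HR, failures kept not ready to Day 14 |
|---|---|---|
| 5% v 5% | about 1 | about 1 |
| 10% v 5% | 0.97 | 0.90 to 0.91 |
| 15% v 5% | 0.93 to 0.94 | 0.81 to 0.82 |
| 20% v 5% | 0.91 | 0.75 |

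The SAP rule shows only part of the arm difference in failures. With equal failures the hazard ratio does not move, but both curves are still too high.

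**The case against.** The strongest objection concerns what is being estimated. Log-rank and Cox analyses that censor competing events validly compare cause-specific hazards, here the rate of readiness among wounds still on study treatment. A reader might infer that the SAP's hazard ratio is simply biased in favour of whichever device fails more often. The documents do not support that. The two hazard-ratio columns above answer different questions, and the lower values depend on assumed rates and on failures never becoming ready. Protocol 5.2.3 foresees a further intervention after withdrawal and repeat debridement, such as closure or graft. If withdrawn wounds became ready at the same rate afterwards, which is equally an assumption, the hazard ratio at 20% v 5% would be 0.92, close to the SAP's 0.91. This part of the objection stands.

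It does not rescue the curve. Observation ends at withdrawal, so only readiness on study treatment can be seen, and the proportion of subjects who reach it is what one minus Kaplan-Meier overstates.

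A second objection is that failures are reported elsewhere: reasons for discontinuation (SAP 9), numbers of events and censored values (SAP 15.2.2), wound closure by arm (SAP 15.3) and adverse events leading to withdrawal (SAP 18.1.2). So it would be wrong to infer that failures are hidden. Those outputs show the failures but do not correct the curve or the median.

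A third is that failures may be rare. Enrolment follows definitive debridement and excludes residual eschar and serious systemic infection. If failures are few and balanced, the comparison hardly changes and the overstatement is small.

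**Conclusion.** The point holds for the Kaplan-Meier curve and the median. Both overstate readiness under study treatment whenever subjects are withdrawn for failure, including when the arms are balanced. At a Kaplan-Meier readiness of 85%, the Day 14 overstatement is about 3 points at 5% failures and about 14 points at 20%. These sizes rest on assumed constant rates and are not a forecast for this trial.

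The log-rank and Cox results are usable if labelled cause-specific. They must not be read as the chance of becoming ready, and they do not carry an arm difference in failures. The endpoint is secondary, so a reader should not infer any effect on the primary non-inferiority test. The change is worth making before database lock, so that it is not chosen with results in view.

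**What to change.** In SAP 15.2.2:

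1. Use the recorded withdrawal reason to define a competing event covering worsening or repeat debridement, target wound needing other treatment, exacerbation, and withdrawal for perceived lack of effect. Fix the classification before database lock, without reference to arm.
2. Report cumulative incidence of readiness by arm, with Gray's test or a Fine-Gray model, in place of the Kaplan-Meier curve, and take the median from it. A simpler approximation keeps these subjects as not ready to Day 14. It matches the Fine-Gray approach only approximately where other early censoring remains.
3. Keep last-image censoring for loss to follow-up and for consent withdrawal unrelated to failure.
4. Label the existing log-rank and Cox results as cause-specific, and show the present rule as a sensitivity analysis.
5. Reconcile the treated-as-missing statement in SAP 15.2.1 with the censoring rules in 15.2.2.

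The cost is one extra derivation and some SAP wording. Protocol 5.2.3 already requires withdrawal reasons to be recorded, so no new data are needed. The downside is that Gray's test and the Fine-Gray ratio are read on the subdistribution scale, which needs a sentence of explanation in the report.
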